### **PRO endpoints**

Data collected with the PRO questionnaires (SF-36v2, Experience of Treatment Benefits and Barriers, and DTSQ (status)) will be scored according to the instruments' respective scoring algorithms into the following endpoints (domains)

- For Experience of Treatment Benefits and Barriers:
  - 'Perceived benefits'
  - 'Perceived barriers'
- For Diabetes Treatment Satisfaction Questionnaire (status):
  - 'Treatment satisfaction'
  - 'Perceived frequency of hypoglycaemia'
  - 'Perceived frequency of hyperglycaemia'
- For SF-36v2:
  - 'Physical Component Summary' score
  - 'Mental Component Summary' score
  - 'Physical functioning'
  - 'Role-physical'
  - 'Bodily pain'
  - 'General health'
  - 'Vitality'
  - 'Social functioning'
  - 'Role-emotional'
  - 'Mental health'

The PRO endpoints will be summarised using descriptive statistics.

## **Biomarker endpoints**

The biomarker endpoints will be analysed using a similar model as described for the primary endpoint except that the corresponding value at baseline will be included as a covariate and the analysis will be made on the original scale. Consequently, treatment means (LSMeans) and treatment differences will be presented with 95% CIs. If the model assumptions are not fulfilled then transformations of the data will be considered, e.g. the change will be calculated on the log-transformed data and the log-transformed value at baseline will be included as a covariate.

The biomarker endpoints will be summarised using descriptive statistics and presented graphically.

### **2.4.1.2 Safety endpoints**

#### **Adverse events, DKA episodes and infusion/injection site reactions**

All adverse events (including DKA episodes and infusion/injection site reactions) will be coded using the latest version of Medical Dictionary for Regulatory Activities (MedDRA). An adverse event will be defined as treatment emergent if the onset of the adverse event occurs on or after the first day of trial product administration.

Treatment emergent adverse events will be summarised by system organ class, preferred term, seriousness, severity and relation to trial product. Separate summaries will be made for treatment emergent DKA episodes and for treatment emergent infusion/injection site reactions. The summaries will be made for the treatment period, for the observation period and for the entire trial period.

Additional information will be recorded on special eCRF pages for selected adverse events. This information will be listed.

All adverse events will be listed and separate listings will be made for DKA episodes and infusion/injection site reactions.

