#### 12.2 Reporting of adverse events

All events meeting the definition of an AE must be collected and reported. This includes events from the first trial-related activity after the subject has signed the informed consent until the end of the post-treatment follow-up period (26 weeks after the end of treatment). The events must be recorded in the applicable eCRF forms in a timely manner, see timelines below and Figure 12–1.

During each contact with the trial site staff, the subject must be asked about AEs and technical complaints, for example by asking: "Have you experienced any problems since the last contact?"

 $^2$  With the exception of hyperglycaemic and hypoglycamic episodes for which reporting starts at V2.

Protocol Trial ID: NN9828-4150 UTN: U1111-1154-7172	CONFIDENTIAL	Date: Version: Status:	07 May 2015 2.0 Final	Novo Nordisk
EudraCT no.: 2014-001215-39		Page:	91 of 141	

All AEs, either observed by the investigator or subject, must be reported by the investigator and evaluated. Novo Nordisk assessment of expectedness is performed according to the following reference documents:

- NN9211 IB, edition 3, 07 August 2013 and updates thereto
- NN9828 IB, edition 1, 2015 and updates thereto

All AEs must be recorded by the investigator on an AE form. The investigator should report the diagnosis, if available. If no diagnosis is available, the investigator should record each sign and symptom as individual AEs using separate AE forms.

For SAEs a safety information form must be completed in addition to the AE form. If several symptoms or diagnoses occur as part of the same clinical picture, one safety information form can be used to describe all the SAEs.

MESIs, regardless of seriousness, must be reported using both the AE form and the safety information form and an MESI form. The MESI form is a form tailored to collect specific information related to the individual MESI.

The AE form for a non-serious AE not fulfilling the MESI criteria should be signed when the event is resolved or at the end of the trial.

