#### 12.3 Follow-up of adverse events

The investigator must record follow-up information by updating the forms in the eCRF.

Follow up information must be reported to Novo Nordisk according to the following:

• **SAEs**: All SAEs must be followed until the outcome of the event is "recovered/resolved", "recovered/resolved with sequelae" or "fatal", and until all queries have been resolved. Cases of chronic conditions, cancer or AEs ongoing at time of death (where death is due to another AE) may be closed with the outcome "recovering/resolving" or "not recovered/not resolved". Cases can be closed with the outcome of "recovering/resolving" when the subject has completed the follow-up period and is expected by the investigator to recover.

The SAE follow-up information should only include new (e.g. corrections or additional) information and must be reported **within 24 hours** of the investigator's first knowledge of the information. This is also the case for previously non-serious AEs which subsequently become SAEs.

- Non-serious AEs: Non-serious AEs must be followed until the outcome of the event is "recovering/resolving", "recovered/resolved" or "recovered/resolved with sequelae" or until the end of the follow-up period stated in the protocol, whichever comes first, and until all queries related to these AEs have been resolved. Cases of chronic conditions, cancer or AEs ongoing at time of death (where death is due to another AE) may be closed with the outcome "recovering/resolving" or "not recovered/not resolved". Cases can be closed with the outcome of "recovering/resolving" when the subject has completed the follow-up period and is expected by the investigator to recover.
- Non-serious AE fulfilling the MESI criteria: Non-serious AE fulfilling the MESI criteria must be followed as specified for non-serious AEs. Follow-up information on MESIs should only include new (e.g. corrections or additional) information and must be reported within 14 calendar days of the investigator's first knowledge of the information. This is also the case for previously reported non-serious AEs which subsequently fulfil the MESI criteria.

The investigator must ensure that the worst case severity and seriousness of an event is kept throughout the trial. A worsening of an unresolved AE must be reported as follow up with reassessment of severity and/or seriousness of the event.

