## 17.4.1.2 Safety endpoints

## Adverse events, DKA episodes and infusion/injection site reactions

All adverse events (including DKA episodes and infusion/injection site reactions) will be coded using the latest version of Medical Dictionary for Regulatory Activities (MedDRA). An adverse

Protocol         Da           Trial ID: NN9828-4150         Ve           UTN: U1111-1154-7172         Sta           EudraCT no.: 2014-001215-39         Pa	Date:         07 May 2015           Version:         2.0           Status:         Final           Page:         114 of 141	Novo Nordisk
--	---	--------------

event will be defined as treatment emergent if the onset of the adverse event occurs on or after the first day of trial product administration.

Treatment emergent adverse events will be summarised by system organ class, preferred term, seriousness, severity and relation to trial product. Separate summaries will be made for treatment emergent DKA episodes and for treatment emergent infusion/injection site reactions. The summaries will be made for the treatment period, for the observation period and for the entire trial period.

Additional information will be recorded on special eCRF pages for selected adverse events. This information will be listed.

All adverse events will be listed and separate listings will be made for DKA episodes and infusion/injection site reactions.

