#### 1.1.3 Type of trial

The trial is a randomised, multi-centre, multinational, placebo-controlled, double-dummy, double-blind, efficacy, safety and PK CPOP trial in subjects with newly diagnosed T1DM with residual beta-cell function. The trial includes four parallel treatment groups, one with NNC0114-0006 12 mg/kg i.v. every 6 weeks and liraglutide 1.8 mg s.c. daily, one with NNC0114-0006 12 mg/kg i.v. every 6 week, one with liraglutide 1.8 mg subcutaneously (s.c.) daily and, one placebo arm randomised in an even ratio. The randomisation will take place not more than 4 weeks from start of screening (V1). The exposure period for NNC0114-0006 and liraglutide in combination or alone is

54 weeks. The primary endpoint (C-peptide) is at week 54 as defined per U.S. FDA and EMA requirements followed by a 26 weeks observation period. All groups will receive insulin treatment according to a treat-to-target (T-T-T) regimen throughout the entire trial. See Figure 1–1 for the schematic trial design.

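### The treatment-emergent rule looks only at onset date, so an adverse event that starts before first dose and worsens on treatment is missing from every treatment-emergent summary

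*SAP*

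**What the plan says.** **Classification.** In SAP 2.4.1.2 (adverse events) an event is "defined as treatment emergent if the onset of the adverse event occurs on or after the first day of trial product administration". Protocol 17.4.1.2 says the same: an "event will be defined as treatment emergent if the onset of the adverse event occurs on or after the" first dosing day. Neither text has a clause for worsening, and SAP section 3, which lists the changes from the protocol, leaves the definition alone.

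**Collection.** Protocol 12.2 collects "events from the first trial-related activity after the subject has signed the informed consent", so an AE can have an onset before any trial product is given.

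**Recording of change.** Protocol 12.3 states: "A worsening of an unresolved AE must be reported as follow up with reassessment of severity and/or seriousness of the event". It gives the same follow-up route to a non-serious event that turns serious ("This is also the case for previously non-serious AEs which subsequently become SAEs"), and adds: "The investigator must ensure that the worst case severity and seriousness of an event is kept throughout the trial".

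**Reporting.** SAP 2.4.1.2 tabulates treatment-emergent AEs only, for the treatment period, the observation period and the whole trial. All other AEs appear in a listing.

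**The concern.** Each rule is ordinary when read alone. Together they leave a gap: the event keeps a pre-dose onset, takes on its worst post-dose severity and seriousness, and is then removed from the tables because of the onset date.

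The part removed is the informative part. Randomisation should balance the AEs that start before dosing. Whether such an event gets worse after dosing can depend on the arm. The number of treatment-emergent AEs is a named safety endpoint, and the by-severity and by-seriousness tables are where a reader compares the arms.

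A gastrointestinal example is the most natural one. Protocol 18.1 reports that 42% of subjects in the liraglutide development programme had a gastrointestinal event, most often early in treatment. Mild nausea that begins during screening and becomes severe after liraglutide is started would be absent from every treatment-emergent table.

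**Working it through.** The documents state no figure on this point, so the check is a trace of one complaint through the rules. The Protocol 2 flow chart puts Visit 1 at Day -28 to Day -14, and SAP 1.1.3 caps the interval from Visit 1 to randomisation at 4 weeks. The window in which an AE can start before dosing is therefore about 2 to 4 weeks per subject.

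Take the same mild complaint, still open at first dose where it began earlier, with a clinically significant worsening after first dose:

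| First appears | Initial record | How the worsening is entered | Onset tested by the rule | In treatment-emergent summaries? |
|---|---|---|---|---|
| Already present at Visit 1 | Concomitant illness (Protocol 8.2.1) | As an AE (Protocol 8.2.1, 12.1) | The worsening, on a natural reading | Yes |
| After Visit 1, before the first dosing day | AE (Protocol 12.2) | Follow-up on the same AE (Protocol 12.3) | Before first dose | **No** |
| On or after the first dosing day | AE | Follow-up on the same AE | On or after first dose | Yes, at worst severity |

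Only the middle row is lost. The first row shows that the protocol already regards worsening of a pre-existing condition as reportable. The result therefore turns on whether the complaint began just before or just after Visit 1, which has no bearing on the safety question.

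The gap does not extend to everything in the safety section:

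- Site reactions to trial product cannot start before dosing.
- Hypoglycaemic and hyperglycaemic episodes are discrete, with maximum durations (Protocol 8.4.2.6 and 8.4.2.7), so they are essentially unaffected.
- For ECG, physical examination, vital signs and laboratory results, Protocol 8.4.5, 8.4.7, 8.4.8 and 8.5 require a clinically significant worsening from or after Visit 1 to be recorded as an AE. How this fits with the follow-up rule when an AE is already open is not stated.

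**Size.** Three rates would be needed: subjects with a pre-dose AE, the share of these unresolved at first dose, and the share that then worsens. The documents give none of them. As an assumption only, with 304 subjects:

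- low: 304 × 0.10 × 0.30 × 0.05 = 0.46 events
- high: 304 × 0.30 × 0.50 × 0.20 = 9.1 events

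Across four equal arms that is about 0.1 to 2.3 per arm. The two ends differ by a factor of 20, which shows that the documents do not determine the number.

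**The case against.** The strongest reply is that no safety information is lost. A reader might infer that these events are never counted anywhere, and the documents do not support that. The event is in the listing of all AEs. Its worst severity and seriousness are kept on the record. If it becomes serious, follow-up is due within 24 hours (Protocol 12.3). The safety committee reviews all reported AEs without a treatment-emergent filter (Protocol 12.7.1). This stands: the fault lies in the analysis tables, not in surveillance or expedited reporting.

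A reader might also take the typical case to be a mild screening infection that the antibody makes worse. Protocol 6.4 bars randomisation with a recent major bacterial infection or with clinically significant signs of any infection, and the dosing-day criteria in Protocol 5.3.1 postpone the infusion on similar grounds. This stands in large part. What remains is non-infectious AEs and infections judged not clinically significant.

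Nor can one infer that some of the affected events will be serious. The assumed share above is for any worsening, and at the low end there is less than one event in all.

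Finally, SAP section 2 allows supplementary analyses, so a separate table of pre-dose AEs that worsened could be produced without touching the definition. That is permission, not a commitment, and the treatment-emergent endpoint would still omit the events.

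**Conclusion.** The concern holds for the treatment-emergent summaries. An AE with onset between consent and first dose that worsens on or after first dose is left out of every one of them, by a stated rule and not by missing detail. The conclusion rests on reading the follow-up rule as keeping the original onset date, which is what its wording implies.

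The number affected cannot be estimated from the documents. It is probably small, given the short window and the infection criteria. It still deserves correction: serious events are usually few, so one or two omissions could be visible in a by-arm table, and the repair is cheap.

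**What to change.** Before the randomisation code break at the interim database lock, extend the definition in SAP 2.4.1.2: an AE is also treatment emergent if it began before first dose and its severity or seriousness increased on or after first dose. Add the change to SAP section 3, and state that the date of the increase places the event in the treatment or observation period.

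That date is needed because the AE record holds only the worst case. The follow-up records and the eCRF audit trail (Protocol 13.1) keep old and new values with the date and time of entry, which identifies the affected records. The date of entry is not necessarily the date of worsening, so a blinded query should confirm it, limited to pre-dose AEs unresolved at first dose.

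Do not instruct sites to enter the worsening as a new AE. That contradicts Protocol 12.3 and would put two records for one event in the listing. It would be workable only if that section were amended to match.

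The cost is one sentence in the SAP and a minor extra data review for a small set of records.

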#### **Hyperglycaemic episodes**

Hyperglycaemic episodes will be defined as treatment emergent if the onset occurs on or after the first day of trial product administration.

The number of treatment emergent hyperglycaemic episodes will be summarised by treatment. The summaries will be made for the treatment period, for the observation period and for the entire trial period.

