Blood samples (11-point profile) will be collected 10 minutes prior to the meal (-10) at meal start (0), and at 15, 30, 60, 90, 120, 150, 180, 210 and 240 minutes after meal start. The blood samples will be assayed for C-peptide and plasma glucose. During the MMTT plasma glucose will be monitored on a validated plasma glucose instrument. If the glucose level exceeds 16.7 mmol/l (300 mg/dl) plasma ketones (betahydroxybutyrate) should be measured on a BG meter.

The subject is allowed to go to the toilet. The number of visits to the toilet should be limited. The subjects are allowed to drink water 2 hours after start of the MMTT. The amount of ingested water should be limited.

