#### 8.4.2.6 Hyperglycaemic episodes

A hyperglycaemic episode is defined as, and confirmed by PG values >16.7 mmol/l (300 mg/dl).

PG should always be measured when there is a suspicion of a hyperglycaemic episode. Multiple (>1) hyperglycaemic values of SMPG >16.7 mmol/l (300 mg/dl) are considered as one hyperglycaemic episode until the SMPG is <16.7 mmol/L (300 mg/dl). One episode is set to a maximum of 24 h for the first SMPG >16.7 mmol/l (300 mg/dl).

All PG values >16.7 mmol/l (300 mg/dl) should be recorded by the subject in the e-diary from visit 2 to visit 89.

The recording should include the following information (layman-language will be used in the ediary to phrase the respective questions ensuring that subjects understand the questions):

- Date and time of hyperglycaemic episode
- The PG level before treating the episode
- Blood ketone value before treating the episode
- Date, time and dose of last liraglutide/placebo administration prior to the episode
- Date, time and dose of last basal insulin administration prior to the episode
- Date, time and dose of last bolus insulin administration prior to the episode
- Whether the episode was symptomatic
- Where there any factors contributing to the hyperglycaemic episode?
  - Recent changes in diet
  - Concomitant infection
  - Recently missed or reduced dose of insulin
  - Other
  - Unknown

Protocol Trial ID: NN9828-4150	CONFIDENTIAL	Date: Version:	07 May 2015 2.0	Novo Nordisk
UTN: U1111-1154-7172 EudraCT no.: 2014-001215-39		Status: Page:	Final 62 of 141	

The subject should measure his/her plasma ketones when plasma glucose values >16.7 mmol/l (300 mg/dl). Subjects will be instructed in how to record the results of the ketone values in the provided e-diaries and should only record the ketone values based on the glucometer measurements.

If the hyperglycaemic episode fulfils the criteria for an SAE then an AE form and a SIF must also be completed in the eCRF.

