# Preparation and conduct of the MMTT

The MMTT will be initiated in the morning after fasting for at least 6 hours. The NNC0114-0006/placebo may be given during the MMTT.

Subjects will be instructed not to take basal insulin after 22.00 the evening before the MMTT. Receipt of insulin boluses is allowed until 2 hours prior to the MMTT.

The MMTT may also be re-scheduled within 1-10 days. Re-scheduling of the MMTT is not considered as an unscheduled visit. Two rescheduling's are allowed per *The* MMTT visit *can be rescheduled twice at a maximum*. If this is *still* not possible the MMTT must be reported as not done. All other assessments at the visit should be conducted as planned including dosing of NNC0114-0006/placebo.

If the plasma glucose value measured at the site before the MMTT is  $\leq$ 3.9 mmol/l (70 mg/dl), the hypoglycaemic episode must be reported in the subject's e-diary. The investigator should consider if the MMTT is appropriate treatment. If the subject needs further treatment the MMTT must will be rescheduled within 1-10 daysRe-scheduling of the MMTT is not considered as an unscheduled visit. Two rescheduling's are allowed per MMTT visit. If this is not possible the MMTT must be reported as not done. All other assessments at the visit should be conducted as planned including dosing of NNC0114-0006/placebo.

Inal ID: NN9828-4150     CONFIDENTIAL     Version:     1.0       UTN: U1111-1154-7172     CONFIDENTIAL     Status:     Final       EudraCT No.: 2014-001215-39     Page:     24 of 27	Protocol Amendment 2 Trial ID: NN9828-4150 UTN: U1111-1154-7172 EudraCT No.: 2014-001215-39	CONFIDENTIAL	Date: Version: Status: Page:	14 March 2016 1.0 Final 24 of 27	Novo Nordisk
---	--	---------------------	---------------------------------------	---	--------------

During the MMTT plasma glucose will be monitored on a validated plasma glucose instrument *using a BG meter*. If the glucose level exceeds 16.7 mmol/l (300 mg/dl) plasma ketones (betahydroxybutyrate) should be measured on a BG meter.

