### 2.3 Primary endpoint

The primary endpoint is  $AUC_{0-4h}$  for a MMTT stimulated C-peptide concentration-time curve at week 54 relative to baseline:  $AUC_{0-4h, C-peptide, 54w} / AUC_{0-4h, C-peptide, baseline}$ .

The  $AUC_{0-4h}$  for MMTT stimulated C-peptide is derived at baseline and at 12, 24, 36, and 54 weeks and is denoted  $AUC_{0-4h, C-peptide, t}$ , where  $t$  is the time of the assessment. Thus,  $t=54$  weeks corresponds to the primary endpoint.

More specifically,  $AUC_{0-4h, C-peptide, t}$  at time 't' will be determined as the area from 0 to 4 hours under the C-peptide concentration profile after a MMTT using the trapezoidal method based on observed concentration values and actual measurement times. If the MMTT is stopped before 4 hours due to hyperglycaemia or hypoglycaemia, the last measured C-peptide concentration will be carried forward for calculation of the primary endpoint. If the MMTT is stopped before 4 hours it will most likely be due to hyperglycaemia as hypoglycaemia is not expected when a high amount of carbohydrates are ingested. Using last observation carried forward (LOCF) will result in an overestimated AUC since the C-peptide response is expected to be at the maximum level during hyperglycaemia. Furthermore, the risk of hyperglycaemia during MMTT will be higher in the placebo group if the active treatments have an effect on beta-cell preservation. Thus, LOCF is considered as a conservative approach. In case the MMTT is stopped before 4 hours for reasons that are not due to hyperglycaemia or hypoglycaemia, the remaining C-peptide concentrations will be set to  $lloq/2$ .

Let  $y_{it}$  denote the value of  $AUC_{0-4h, C-peptide, \Delta t}$  evaluated relative to baseline at time  $t$  for subject  $i$ , i.e.

$$y_{it} = \text{AUC}_{0-4h, \text{ C-peptide}, \Delta t} = \text{AUC}_{0-4h, \text{ C-peptide}, t} / \text{AUC}_{0-4h, \text{ C-peptide}, \text{ baseline}}$$

log of  $y_{it}$  will be analysed using an (MMRM) including all available assessments over time with treatment, stratum and sex as factors and  $\ln(\text{AUC}_{0-4h, \text{ C-peptide}, \text{ baseline}})$  and age at baseline as covariates (see [Table 2-2](#)). The interaction between all variables and visit (week) will be included in the model as fixed effects.

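### Glucose above 16.7 mmol/l provoked by a scheduled meal test is not separated from the treatment-emergent hyperglycaemia counts, and by the SAP's own reasoning it may fall unevenly across arms

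*SAP*

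**What the plan says.** **Definition and recording.** Protocol 8.4.2.6 defines a hyperglycaemic episode by plasma glucose above 16.7 mmol/l and adds: "All PG values >16.7 mmol/l (300 mg/dl) should be recorded by the subject in the e-diary from visit 2 to visit 89". Repeated high values are merged into one episode, capped at 24 hours. The listed contributing factors are diet, infection, missed or reduced insulin, other and unknown. There is no entry for a meal test.

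**Treatment emergence and analysis.** SAP 2.4.1.2 uses onset date only: "Hyperglycaemic episodes will be defined as treatment emergent if the onset occurs on or after the first day of trial product administration". The analysis is descriptive: "The number of treatment emergent hyperglycaemic episodes will be summarised by treatment", for the treatment, observation and entire trial periods.

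**The meal test.** Protocol 8.3.1 foresees the same threshold being crossed during the MMTT: "If the glucose level exceeds 16.7 mmol/l (300 mg/dl) plasma ketones (betahydroxybutyrate) should be measured on a BG meter". Protocol Amendment 2 has glucose monitored with a BG meter during the test. For a low value found before the test, that amendment says "the hypoglycaemic episode must be reported in the subject's e-diary". It has no matching sentence for high values during the test.

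**Expected direction.** SAP 2.3, when justifying carry-forward for stopped tests, says "the risk of hyperglycaemia during MMTT will be higher in the placebo group if the active treatments have an effect on beta-cell preservation".

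**The concern.** The MMTT is a deliberate glucose challenge. Under Protocol 8.3.1 (as amended by Amendment 2) the test starts at a glucose of at most 9.0 mmol/l, after basal insulin has been withheld and with no recent bolus. Mealtime insulin resumes only with the meal after the test. A value above 16.7 mmol/l in the intervening four hours therefore arises during a trial procedure and says little about glycaemic safety in daily life.

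If such values enter the episode count, a listed safety endpoint contains a component driven by the same test that supplies the primary endpoint. If the drugs work, that component should be larger on placebo. A reader of the summary table could then credit the active arms with a safety advantage that partly restates the C-peptide result.

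**Working it through.** **1. The plan's own figures.** None is given for hyperglycaemic episodes. The design figure is the power for the primary endpoint (SAP 2.1: 80.4% at 60 completers per arm). Difference = ln(0.98/0.65) = 0.411; SE = √((1² + 0.5²)/60) = 0.144. The noncentral t with Satterthwaite degrees of freedom gives 80.3%, so the figure reproduces. Nothing below affects it.

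**2. Do the rules capture meal-test readings?**
- Threshold: the same 16.7 mmol/l in Protocol 8.4.2.6 and in the MMTT text.
- Recording: all values from Visit 2 to Visit 89, with MMTT days not excepted. Visit 2 is itself an MMTT visit.
- Measurement: a BG meter is in use during the test (Amendment 2).
- SAP: adds a date criterion and nothing else.

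Read literally, the rules capture such readings. No sentence excludes, flags or separately tabulates them, and no sentence expressly says that they become diary episodes.

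**3. Upper bound on the count.** Post-dose MMTTs are at weeks 12, 24, 36 and 54 (SAP 2.3) and at weeks 65 and 80 (protocol flow chart). The Visit 2 test precedes dosing and cannot be treatment emergent. The SAP ends the treatment period on the date of Visit 63, so a week-54 test held that day falls inside it. A test re-scheduled after that date (Protocol 8.3.1 allows 1 to 10 days) would fall in observation. Merging and the 24-hour cap make it about one episode per test.

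- Treatment period: 4 × 1 = 4 per completer. That is 4 × 60 = 240 per arm at 60 completers, or 4 × 76 = 304 at 76 randomised (304/4).
- As a rate: 54/52.18 = 1.035 years; 4/1.035 ≈ 3.9 per patient-year.
- Observation period: 2 per completer, or 120 per arm at 60 completers.

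**4. Illustrative effect on the ratio between arms.** Two figures are missing from the documents and are assumed here: the share of tests above 16.7 mmol/l on placebo (p_P) and active (p_A), and a background rate b, equal in both arms.

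Ratio = (1.035b + 4p_A) / (1.035b + 4p_P). The true ratio is 1.00.

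Example with b = 5, p_P = 0.4, p_A = 0.2: (5.17 + 0.8)/(5.17 + 1.6) = 0.88. The placebo count rises by 1.6/5.17 = 31%.

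| b per patient-year | 10% v 5% | 40% v 20% | 80% v 40% | 40% v 40% |
|---|---|---|---|---|
| 1 | 0.861 | 0.696 | 0.622 | 1.00 |
| 5 | 0.964 | 0.882 | 0.809 | 1.00 |
| 10 | 0.981 | 0.933 | 0.882 | 1.00 |
| 20 | 0.991 | 0.964 | 0.933 | 1.00 |
| 50 | 0.996 | 0.985 | 0.971 | 1.00 |

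The distortion runs from negligible to large, depending on inputs that the documents do not supply. With equal shares all arms inflate alike and the ratio is unchanged.

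**The case against.** The strongest objection is that counting is an inference. Protocol 8.4.2.6 describes values entered by the subject, and its merging rule speaks of self-measured glucose. MMTT glucose is monitored at the site. The protocol's list of items to document for the MMTT contains no hyperglycaemia diary entry. When the sponsor wanted an MMTT-day reading in the diary, it wrote a sentence for it, and that sentence covers only low values before the test. Part of this stands: the pre-test hypoglycaemia sentence does not establish that in-test high values are entered. The self-measurement wording does not settle the matter the other way, because the same documentation list uses SMPG for the pre-meal reading taken at the site. Silence also leaves sites free to record differently.

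A reader might also infer that the plan inflates the placebo count. The documents do not support that as a flat statement. All arms have the same MMTT schedule, and the SAP's expectation of more test hyperglycaemia on placebo is conditional on efficacy. Better beta-cell function could lower everyday hyperglycaemia too, so some link with the primary endpoint would exist without the MMTT.

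Nor is any inference at risk. The SAP plans no model, interval or test for this count, and it is not among the key endpoints marked for disclosure, unlike DKA and hypoglycaemia to week 54. Treatment emergence here is defined by time and not by cause, which fits the protocol's definition of an adverse event.

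Finally, dropping these episodes from the main summary would also drop in-test events with raised ketones, including those that oblige the site to stop the test. That argues for showing counts both ways.

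**Conclusion.** The point holds in a limited form. Protocol 8.4.2.6 and SAP 2.4.1.2 contain no exception for glucose above 16.7 mmol/l provoked by a scheduled MMTT, so such readings qualify as treatment-emergent episodes under the rules as written. The bound is about four per completer in the treatment period and two in observation, with the week-54 test moving to observation if it is re-scheduled after the Visit 63 date. If the active treatments preserve beta-cell function, the SAP's own reasoning puts more of these episodes on placebo, and the descriptive comparison would partly repeat the efficacy test.

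The conclusion rests on the literal reading of the recording rule and on about one episode per test. The actual size cannot be derived from the documents. It would be wrong to conclude that these readings are certain to have been counted, that the placebo count is inflated whatever the drug effect, or that an error rate is affected.

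**What to change.** In SAP 2.4.1.2, before the randomisation code break:

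- Flag every hyperglycaemic episode with onset between MMTT meal start and the last MMTT blood sample. The last sample is the better end point, because the protocol's documentation list includes actual sample times but no separate stop time for a test ended early.
- Tabulate the flagged episodes by treatment as test-provoked.
- Present the hyperglycaemic episode summaries for each period both with and without them, so that no safety event leaves the report.

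MMTT date, meal times and sample times are already recorded (Protocol 8.3.1), as are episode date and time (Protocol 8.4.2.6). The cost is a short addition to the SAP, a date-time merge and one extra table. No new data are needed.
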